[1669332] High-frequency sacral root stimulation to improve bladder and bowel emptying following SCI

Funding Agency: Department of Veterans Affairs

Principal Investigator/Study Chair: [name]

Version 1.6
2 February 2023

Abstract

This is a 2-year case series study. Study participants will act as their own controls. This study will determine if sacral root stimulation at 600 Hz limits urethral sphincter contractions in individuals with SCI who have already been implanted with a Finetech-Brindley SARS system. The Finetech-Brindley SARS system is an FDA-approved device (Humanitarian Use Device) and we have received an IDE for testing this device at 600 Hz. In an initial visit lasting about 1 hour, we will complete an informed consent process to enroll the participant and collect a urine sample to test for a UTI. In a second visit lasting about 4 hours, we will conduct experiment procedures. Bladder and urethral sphincter pressures will be recorded using standard clinical urodynamics techniques. In a urodynamics laboratory, we will collect baseline data in response to the typical stimulation parameters that the participant uses for their daily bladder management. We will then test 600 Hz stimulation to determine whether this results in reduced sphincter contraction (Aim 1). The Finetech-Brindley device can also be programmed to achieve bowel emptying and return of bowel control is an extremely high priority for individuals with SCI [7]. Therefore, we will leverage the opportunity of this pilot study to determine if 600 Hz sacral root stimulation also has the potential to improve bowel emptying by reducing anal sphincter pressure (Aim 2). Participants will be asked to participate in experiments for both Aim 1 and Aim 2. Study participants who are Veterans will be consented and tested at the Cleveland VA Medical Center. Participants who are not Veterans will be consented and tested at the MetroHealth Medical Center. An IRB protocol for this study has already been approved at the MetroHealth Medical Center.

List of Abbreviations

CRC – Clinical Research Center
DSD – detrusor-sphincter dyssynergia
FES – functional electrical stimulation
LSCVAMC – Louis Stokes Cleveland Department of Veterans Affairs Medical Center
NIDDK - National Institute of Diabetes and Digestive and Kidney
NIH – National Institute of Health
SARS - sacral anterior root stimulation
SCI - spinal cord injury
SCI&D - Spinal Cord Injury & Dysfunction
TDL - Technical Development Laboratory

2.0 Introduction

Spinal cord injury (SCI) leads to neurogenic bladder dysfunctions, and often includes difficulty with emptying the bladder due to detrusor-sphincter dyssynergia (DSD). Current bladder management strategies include catheterization, pharmaceuticals, and/or surgery, but these interventions insufficiently meet individuals' needs. The neurogenic bladder can be emptied using sacral anterior root stimulation (SARS) with electrodes implanted on the sacral nerves to produce bladder contractions. However, this emptying can be impeded by reflex contractions of the urethral sphincter. The sacral sensory roots are typically transected (rhizotomy) to reduce these reflex contractions, but this rhizotomy also impairs desirable reflexes (e.g., sexual function) and sacral sensation if present. Experiments in animals have shown that sacral root stimulation at 600 Hz can inhibit urethral sphincter activity, which has the potential. This approach could be used in lieu of the rhizotomy to improve bladder emptying efficiency.

3.0 Objectives

The objective of this study is to test the potential effectiveness of 600 Hz sacral root stimulation to limit urethral sphincter activity in individuals with neurogenic bladder dysfunction (Aim 1). We hypothesize that sacral root stimulation at 600 Hz will result in lower urethral sphincter pressures compared to pressures in response to stimulation at the lower frequencies that are typically used for SARS. We will also test if this stimulation similarly limits anal sphincter activity (Aim 2). Individuals will already have received an implanted SARS device and will have also received a rhizotomy.

5.0 Study Procedures

5.1 Study Design

In this 2-year case series study, we will enroll 8 participants, male or female, who have SCI and who already use implanted sacral root anterior stimulation to manage their bladder. Participants will act as their own controls.

If a participant is a Veteran, then they will complete study visits at the Cleveland VA Medical Center. If they are not a Veteran, then they will complete study visits at MetroHealth Medical Center for which we already have an approved IRB protocol.

During an initial study visit, expected to take about one hour, we will obtain informed consent. Then a sample of urine will be collected and tested to determine if they have a urinary tract infection.

In the days following this initial visit, subjects will be prescribed an antibiotic, which they will pick up from Pharmacy, to take in the days before and after participation in this study to prevent a urinary tract infection. We will contact subjects in the days leading up to the second visit to remind them of the antibiotic.

A second study visit will then occur 2-30 days later and last about 4 hours. Stimulus waveforms for urethral sphincter inhibition will be tested in the clinical laboratory in a single session. We will not need to conduct new surgeries or implant procedures. The primary outcome measure is urethral sphincter pressure, and additional outcome measures include bladder pressure, rectal pressure, and bladder volume as measured in clinically standard urodynamics examination. The primary outcome measure for Aim 2 is anal sphincter pressure.

Clinical Impact

This study represents the first attempt to limit urethral sphincter contraction via 600 Hz stimulation of sacral roots in human participants. This approach using 600 Hz sacral root stimulation has successfully demonstrated voiding in chronic spinalized dogs, but has not been tested in humans. The Finetech-Brindley external controller has been modified to be capable of producing stimulation up to 600Hz. An Investigational Device Exemption has been obtained from the FDA to test this approach in human participants. Thus, one significant advantage of our study is that we will use this modified external controller to communicate with the already-implanted components of the system without new surgical procedures or significant risks. A second key advantage is that, because they have had a posterior rhizotomy, we can determine the stimulation parameters for activating and potentially limiting sphincter activity directly via the motor nerves, without confounding effects from sacral spinal reflexes. If this project is successful, these parameters can be applied in a future project to individuals who can have a stimulator implanted without rhizotomy, to determine if reflex activation of the sphincter can also be reduced. We understand that future work without rhizotomy will include the influence of reflex pathways, and this study may help us understand that influence by having this negative control. A future project would also then refine this approach by combining 600 Hz stimulation to reduce sphincter pressure with 20 Hz stimulation to evoke bladder contraction.

This project could have a high impact for individuals with neurogenic bladder dysfunction. It would help to address one of the highest priorities of individuals with SCI – restoration of bladder function - and help to address some of the biggest costs and health risks associated with managing neurogenic bladder by potentially improving bladder emptying without the need for catheters. There is a high potential for clinical translation because this approach takes advantage of existing technologies.

If this project demonstrates evidence of urethral sphincter pressure reduction in response to 600 Hz stimulation, then we will propose in a subsequent project to apply 600 Hz stimulation to individuals with SCI in whom sacral reflexes are intact. We would implant a SARS device without the rhizotomy, and determine if reflex contractions of the sphincter can be prevented during bladder emptying. In this way, we plan to achieve efficient, catheter-free, on-demand bladder emptying using sacral root stimulation without the need for a posterior rhizotomy.

5.2 Recruitment Methods

Eight participants will be enrolled, both men and women. Participants will be recruited from a pool of approximately 50 individuals who have already been implanted in Cleveland with the Finetech-Brindley SARS system. Individuals who are already implanted with the SARS system receive regular follow-up contact regarding their system. Our clinical colleagues will ask them about their interest in this study. Individuals who express interest will then be contacted by our study team for study enrollment. We conservatively estimate that at least 50% of these individuals can be reached for follow-up and 50% of those individuals will be willing to participate in this study. We have already received confirmation from 4 such individuals of their interest in participating in this work. Therefore, we are confident that we will not have difficulty recruiting for this study.

Study subjects will be compensated \$75 for their participation via Greenphire ClinCard. This compensation rate is consistent with subject honoraria at our local site. They will receive Payment after each visit, including \$25 if they complete the first visit and \$50 if they complete the second visit. If the participants do not have a private vehicle, transportation will be provided to them.

5.3 Informed Consent Procedures

The PI ([name]), or other staff authorized to obtain informed consent, will explain the study in person, answer questions, and obtain informed consent for participation in this study. The consent process will take place in privacy in a quiet room. The study goals and an overview of the experiment will be reviewed with each participant. Special care will be taken to inform the participant of all the potential risks of participation and that they may choose to withdraw from the study at any point. HIPAA guidelines will be followed by all study staff. For VA study participants, signed consent forms will be stored in a locked drawer in a locked room (B-E336). Consent will be obtained during the initial visit. The consent form will include contact information for the research team should the subject have further questions during the study.

5.4 Inclusion/Exclusion Criteria

Inclusion:

- Uses a SARS System with rhizotomy for bladder management
- Suprasacral SCI
- Neurologically stable
- Skeletally mature

Exclusion:

- Active, symptomatic urinary tract infection (UTI)
- Active sepsis
- Open pressure injuries on or around the pelvis

- Bleeding diathesis
- Significant urethral trauma, erosion, or stricture

5.5 Study Evaluations

We will use standard clinical urodynamics methods for data collection. We will use an FDA-approved modified external controller to communicate with the already-implanted components of the system, so no new surgeries or other procedures are required. The device has been modified to achieve frequencies up to 600 Hz and this modification was approved by the FDA in an IDE. We will document their normal daily usage device settings for reference, including stimulation amplitude, pulse width, frequency, and on/off cycle duration.

Clinical Urodynamics and Anorectal Manometry Procedure: A standard catheter will be inserted into the bladder via the urethra and the bladder will be emptied. This catheter will be removed and then a second catheter, which can measure bladder and urethral pressures, will be inserted. This catheter will also have a lumen for filling the bladder with sterile saline. A balloon catheter inserted in the rectum will be used to reflect abdominal pressure and distinguish bladder pressures due to detrusor contraction versus bladder pressures due to abdominal activity. This balloon catheter will measure rectal pressure. It will also have pressure transducers at the anal sphincter to measure anal sphincter pressure. Surface electromyogram (EMG) electrodes will be applied to the anal sphincter to monitor pelvic floor muscle contractions. Infused volumes will be controlled via an infusion pump. EMG and pressure signals will be monitored on a clinical urodynamic system. The participant's bladder will be infused with sterile saline while measuring bladder, urethral sphincter, and rectal pressures.

Sacral Anterior Root Stimulation: We will set the stimulation parameters for the implanted stimulator, including stimulation amplitude and frequency, using a modified Finetech-Brindley external controller unit. The frequency will be set either to 600 Hz or to the low frequency that the participant typically uses for emptying their bladder, which is usually 20 Hz. We will use the participant's own power transmission coil. The receiver coil and electrodes will already have been implanted. The pulse width will not be changed from the participant's normal setting.

Aim 1: Determine if 600 Hz sacral root stimulation limits contraction of the urethral sphincter.

During visit 2, in a single session, we will first administer SARS using the stimulation parameters (i.e., frequency, pulse width, and amplitude) that the study participant typically uses to empty their bladder and has been for years. The purpose is to characterize the usual level of urethral sphincter and bladder pressure during their bladder emptying routines and collect these baseline data.

We will also have a frame of reference for stimulation amplitude for testing 600 Hz stimulation.

We will then decrease the stimulation amplitude and identify the threshold amplitude to achieve urethral sphincter contraction at low frequency, which will be compared to the threshold amplitude to evoke bladder contraction. The motor efferents innervating the urethral sphincter are significantly larger in diameter than the motor efferents innervating the bladder, so the thresholds for activating the bladder are higher than for activating the urethral sphincter. These thresholds amplitudes at low frequency will give us additional context for evaluating the recruitment of urethral sphincter and bladder pressures in response to sacral stimulation.

We will then test stimulation at 600 Hz. 600 Hz stimulation will first evoke a brief (~1-2 second) onset respond and then the urethral pressure is expected to return to baseline. The stimulation amplitude will be set to 0 mA and gradually increased to determine the threshold amplitude for evoking an initial onset response of the urethral sphincter. We will continue to increase the stimulation amplitude until we have achieved maximal urethral sphincter pressure onset response. Stimulation will be maintained for up to 10 seconds with at least 30 seconds rest between stimuli. Once this recruitment curve is established, we will repeat stimulation at threshold, 50% maximal recruitment, and 90% maximal recruitment for up to 30 seconds to measure reduction of urethral sphincter pressures.

Aim 2: Determine if 600 Hz sacral root stimulation limits contraction of the anal sphincter.

This aim has the same design as Aim 1 but will focus on bowel function. Data for this aim will be measured during the same session as Aim 1. We will administer SARS using the stimulation parameters and pattern that the participant typically uses to empty their bowel and has been for years. These data will give us context for evaluating effects on bowel function.

We will then test stimulation at 600 Hz. This testing can be done simultaneously with 600 Hz testing for Aim 1. The stimulation amplitude will be set to 0 mA and gradually increased to determine the threshold amplitude for evoking an initial onset response of the anal sphincter. We will continue to increase the stimulation amplitude until we have achieved maximal anal sphincter pressure onset response. Stimulation will be maintained for up to 10 seconds with at least 30 seconds rest between stimuli. Once this recruitment curve is established, we will repeat stimulation at threshold, 50% maximal recruitment, and 90% maximal recruitment for up to 30 seconds to measure reduction of anal sphincter pressures.

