5.6 Data Analysis

Outcomes from urodynamics data will be used to determine the effect of electrical stimulation on limiting urethral and anal sphincter pressures. Distributions of pressures without and with 600 Hz and 20 Hz stimulation will be compared with an ANOVA and a significance level of 0.05. We expect to observe a lower level of urethral and anal sphincter pressure in response to sacral stimulation at frequencies of 600 Hz compared to the low stimulation frequency that participants typically use.

Potential Limitations and Alternative Solutions

If 600Hz sacral stimulation in humans fails to limit urethral and anal sphincter activity compared to what is evoked at low frequency, then we will need to consider alternative stimulation strategies in future studies. We acknowledge that another potential approach using kilohertz frequency stimulation could be considered. Our group and others have tested kilohertz frequency sinusoidal waveforms extensively preclinically to block nerve conduction. This could be another alternative to the rhizotomy, but it would require development and regulatory approval of a new implantable stimulation system that can safely deliver stimulation in the kilohertz frequency range for human testing [14]– [18].

We do not expect to experience significant technical challenges because (1) we are using a SARS system that study participants have been successfully using for years and (2) we are using research methods that we have successfully used for years to collect these data [19], [20]. We may find that the external controller does not deliver sufficient charge to achieve sphincter reduction at elevated stimulation frequencies. This is unlikely because the amplitude required to avoid contraction at 600Hz frequencies is not significantly higher than the amplitude to achieve activation at lower amplitudes.

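### In Aim 1 every low-frequency bladder run precedes the 600 Hz runs, so the size of the planned difference is confounded with any session drift in evoked sphincter pressure

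*Combined protocol and SAP*

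**What the plan says.** The study is a case series of eight participants who serve as their own controls (section 5.1). Section 5.5, Aim 1, fixes the order within the single session of visit 2:

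1. Usual bladder settings: "During visit 2, in a single session, we will first administer SARS using the stimulation parameters" that the participant already uses.
2. A low-frequency threshold search, with amplitude stepped down.
3. "We will then test stimulation at 600 Hz": "The stimulation amplitude will be set to 0 mA and gradually increased to determine the threshold amplitude for evoking an initial onset response", and on up to the maximal onset response.
4. Repeat 600 Hz runs of up to 30 seconds at threshold, 50% and 90% of maximal recruitment, to measure the pressure reduction.

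The Abstract gives the same order. Neither place describes a varied order or a return to the bladder low-frequency setting after 600 Hz. Within a 600 Hz train the plan foresees a brief "onset respond and then the urethral pressure is expected to return to baseline".

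For Aim 2, "This aim has the same design as Aim 1 but will focus on bowel function". The usual bowel settings are followed by 600 Hz, which may be tested at the same time as the Aim 1 600 Hz block. The text does not say where the bowel-setting run falls relative to that block.

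Section 5.6 states the analysis: "Distributions of pressures without and with 600 Hz and 20 Hz stimulation will be compared with an ANOVA" at the 0.05 level. It adds: "We expect to observe a lower level of urethral and anal sphincter pressure in response to sacral stimulation at frequencies of 600 Hz" than at the participant's usual low frequency. No order or time term is mentioned, and the limitations text does not discuss order, fatigue or drift.

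**The concern.** The hypothesis in section 3.0 is a lower urethral sphincter pressure at 600 Hz than at low frequency, tested within participants. In Aim 1 every low-frequency bladder reading comes before every 600 Hz reading, so frequency and time in session change together. If evoked sphincter pressure falls during a visit of about 4 hours, for whatever reason, the fall adds to the apparent benefit of 600 Hz. No later analysis of that contrast can take it out, because no participant has a late low-frequency reading.

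What rests on the result is the next step. The Clinical Impact text in section 5.1 says: "If this project demonstrates evidence of urethral sphincter pressure reduction in response to 600 Hz stimulation", the investigators will propose a further project in people with intact sacral reflexes, implanting the device without rhizotomy.

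**Working it through.** **Inputs from the documents:** n = 8, own controls (5.1); order of runs (5.5); significance level 0.05 (5.6). The documents give no SD, effect size, drift size or power calculation, so there is no planned figure to reproduce.

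**Step 1, the structure.** Let f be the true fall in pressure due to 600 Hz, and D the fall in evoked pressure from the first low-frequency reading to the 600 Hz runs. The mean of low frequency minus 600 Hz then estimates f + D. With one fixed order and no closing run, f and D cannot be estimated separately from this contrast. This does not depend on the size of D.

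**Step 2, illustration of size (assumptions).** A paired t-test stands in for the ANOVA: two-sided 0.05, 7 df, critical t = 2.365. The unit is the SD of one paired difference. The smallest significant mean fall is 2.365/√8 = 0.836 SD. With f = 0, the chance of significance follows a noncentral t with noncentrality D√8:

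| Assumed D | D√8 | False significance |
|---|---|---|
| 0.25 | 0.707 | 9.4% |
| 0.5 | 1.414 | 23.2% |
| 1.0 | 2.828 | 68.1% |

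**Step 3, with a closing run and the two-reading mean as comparator.** Each reading has SD 1/√2, so the SD of (two-reading mean minus 600 Hz) is √(0.25 + 0.5) = 0.866. The bias is D minus half the fall seen at the last reading, and the noncentrality is bias × √8/0.866.

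| Shape of drift | Fall at last reading | Bias | D = 0.5 | D = 1.0 |
|---|---|---|---|---|
| Linear, 600 Hz runs midway | 2D | 0 | 5.0% | 5.0% |
| Linear, runs at 80% of elapsed time | D/0.8 = 1.25D | 0.375D | 8.3% | 18.6% |
| Levelled off before the 600 Hz runs | D | 0.5D | 10.9% | 29.3% |

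The three rows share the same D but imply different total falls over the session.

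**Step 4, what the closing run can and cannot do.**
- The first-to-last change has SD 1, so its 95% half-width is 2.365/√8 = 0.84 SD.
- For a true effect of 1 SD and no drift, power is 68.1% with the initial reading and 79.9% with the two-reading mean (1/0.866 = 1.155).
- If 600 Hz carries over and lowers the last reading by c, the two-reading contrast becomes (1 − c/2)/0.866. With c = 0.25 power is 69.0%; with c = 0.5 it is 55.9%.
- The last reading alone, for a true 1 SD effect, gives 68.1% with no drift. At D = 1 with linear drift and runs at 80%, the net difference is 1 + 1 − 1.25 = 0.75 and power is 44.9%. With runs midway it is 1 + 1 − 2 = 0, leaving 2.5% in the hypothesised direction.

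**The case against.** The strongest answer is that the plan already holds evidence that slow drift could not easily produce.

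- Section 5.6 includes pressure without stimulation as a level of the ANOVA, so 600 Hz against no stimulation, the return-to-baseline comparison, falls within the planned analysis.
- If 600 Hz behaved like low frequency, a train of up to 30 seconds should show sustained contraction. An onset followed by a fall within seconds is not what drift over a session looks like.
- The amplitude is re-titrated from zero just before the measurement runs. That limits threshold or coupling drift, and the maximal onset shows that the sphincter can still contract.
- Low frequency comes first for a stated reason: it is the baseline and the frame of reference for amplitude.

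All of this stands, and it rules out the stronger reading that a reader might infer, namely that the study cannot tell a 600 Hz effect from drift at all.

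Three gaps remain. The 50% and 90% levels are fractions of the maximum reached at that later time, so re-titration does not correct a weaker contraction. An onset of 1 to 2 seconds does not show what sustained low-frequency pressure would then have been. And unstimulated pressure can reveal drift in resting tone but not in evoked pressure. The onset-versus-sustained contrast is not named in section 5.6.

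It is also fair that the percentages merely restate assumed drifts, that a paired t-test replaces an ANOVA with three 600 Hz amplitudes, and that this is a small pilot whose positive result leads only to a proposal.

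**Conclusion.** The point holds for the size of the across-frequency difference in Aim 1: it is fully aliased with time in session, and a downward drift would act in the hypothesised direction. A complete return to resting pressure at 600 Hz would still be persuasive; a partial reduction would be ambiguous.

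A reader might also infer that drift is present, or that the false-positive rate here is 23% or 68%. The documents support neither. They give no drift, no SD and no interval between the compared runs, and the percentages hold only for the assumed D in a paired t-test with n = 8. For Aim 2 the order is less clear, because the place of the bowel-setting run is not stated. The change is a cheap improvement rather than a condition for the study to be useful.

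**What to change.** - Keep the initial low-frequency run. Add one closing low-frequency run per aim, after the 600 Hz runs, at the participant's same usual settings, and record time and bladder volume.
- List both readings for each participant and report the first-to-last change with its confidence interval.
- Report the 600 Hz contrast against the initial reading and against the two-reading mean. The mean should not be the sole comparator, since carry-over can make it the weaker of the two. Give the contrast against the last reading as a sensitivity analysis that cannot veto a finding, because it can miss a true effect.
- In section 5.6, name sustained 600 Hz versus no stimulation, and onset versus sustained pressure within each 600 Hz train, as reported contrasts. These need no extra stimulation.
- In Aim 2, state where the bowel-setting run falls relative to the Aim 1 600 Hz block.

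The cost is protocol wording, one extra run per aim with catheters already in place, a slightly longer session and possibly refilling. The limits should be stated: carry-over from 600 Hz may lower the closing reading, averaging corrects only roughly linear drift, and the drift estimate is coarse at n = 8 (about ±0.84 SD), so a non-significant change does not show that drift is absent. The amplitudes used at the two frequencies may differ, and that remains a separate limit which a closing run does not remove.

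### The three-condition ANOVA in 5.6 does not test the 600 Hz versus low-frequency hypothesis, and the runs, participant term and time window for that comparison are not stated

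*Combined protocol and SAP*

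**What the plan says.** The hypothesis in section 3.0 is that "sacral root stimulation at 600 Hz will result in lower urethral sphincter pressures compared to pressures in response to stimulation at the lower frequencies" typically used for SARS. Section 5.6 repeats this as the expected result for both sphincters. Its discussion of limitations turns to alternative strategies "If 600Hz sacral stimulation in humans fails to limit urethral and anal sphincter activity compared to what is evoked at low frequency".

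The low-frequency run in 5.5 (Aim 1) uses the usual setting: "we will first administer SARS using the stimulation parameters (i.e., frequency, pulse width, and amplitude) that the study participant typically uses to empty their bladder". Amplitude is then stepped down to find thresholds, which are described as context. For 600 Hz, amplitude is ramped from 0 mA to the maximal onset response, and then "we will repeat stimulation at threshold, 50% maximal recruitment, and 90% maximal recruitment for up to 30 seconds". Of the other parameters, "The pulse width will not be changed from the participant's normal setting". The usual amplitude has only this role: "We will also have a frame of reference for stimulation amplitude for testing 600 Hz stimulation". Aim 2 is said to have the same design, with the bowel setting as its low-frequency run. It does not write out a low-frequency step-down.

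The whole of the stated test in 5.6 is: "Distributions of pressures without and with 600 Hz and 20 Hz stimulation will be compared with an ANOVA and a significance level of 0.05".

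**The concern.** The hypothesis concerns one difference, 600 Hz against low frequency. An ANOVA with a no-stimulation condition tests whether any of three means differ. Usual stimulation is expected to contract the sphincter, so the test can be significant whatever 600 Hz does.

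Section 5.6 leaves open three further things that determine the answer:

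- **Which runs.** Three 600 Hz levels are held, each defined on the 600 Hz onset curve. The usual-setting run is defined by the participant's routine. Nothing requires a common amplitude, so a difference between two such runs could come from amplitude, frequency or both.
- **Participant term.** Participants are their own controls by design (5.1), but the described ANOVA does not carry this.
- **Window.** An onset contraction of about 1-2 seconds is expected before pressure returns to baseline. A peak-based summary would show no reduction even under complete suppression.

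The result bears on whether other stimulation strategies are considered and on the follow-on work without rhizotomy described in 5.1.

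**Working it through.** The plan gives no power, SD or effect size, so there is no figure to reproduce. From the documents: 8 participants, alpha 0.05, three conditions. **Assumed:** a scale in percent of maximal evoked sphincter pressure, and an SD of paired differences of 20, 30 or 40 points. Everything below is illustration.

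**1. Does the three-condition test answer the question?**

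Take a within-participant F test with 2 and 14 degrees of freedom; the critical value is 3.739. Residual variance = SD²/2, that is 200, 450 or 800. Noncentrality = 8 × (sum of squared deviations of the three means) / residual variance.

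- 600 Hz does nothing, amplitude matched: means (none, low, 600 Hz) are 0, 50, 50. The grand mean is 33.3, and the sum of squares is 33.3² + 2 × 16.7² = 1,667.
- 600 Hz abolishes the contraction: means 0, 50, 0. The grand mean is 16.7, and the sum of squares is again 1,667.

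| SD | Noncentrality | Rejects, 600 Hz does nothing | Rejects, 600 Hz abolishes |
|---|---|---|---|
| 20 | 8 × 1,667/200 = 66.7 | 100% | 100% |
| 30 | 8 × 1,667/450 = 29.6 | 99.4% | 99.4% |
| 40 | 8 × 1,667/800 = 16.7 | 91.5% | 91.5% |

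The two opposite truths give the same rejection rate. This step keeps amplitude matched, so it shows a limit of the omnibus test and says nothing about amplitude.

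**2. What does a direct paired contrast do?**

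Noncentral t with 7 degrees of freedom, two-sided 0.05, noncentrality = difference/SD × √8. The table gives the probability of significance in the direction of the difference.

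| Difference (points) | SD 20 | SD 30 | SD 40 |
|---|---|---|---|
| 0 | 2.5% | 2.5% | 2.5% |
| 5 | 8.9% | 6.1% | 4.9% |
| 10 | 23.1% | 12.7% | 8.9% |
| 30 | 95.1% | 68.1% | 44.8% |
| 50 | 100% | 98.0% | 85.6% |

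- Matched amplitude, equal recruitment, no frequency effect: 600 Hz is favoured 2.5% of the time. If 600 Hz abolishes a 50-point contraction, power is 86% to 100%.
- Unmatched, no frequency effect: the spurious difference is the recruitment at the usual setting (U) minus that at the chosen 600 Hz level. At the 50% level, U = 80 gives +30, favouring 600 Hz. At the 90% level, U = 60 gives -30, favouring low frequency equally often. At U = 50 and U = 90 respectively there is no bias. The documents do not give U.

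**3. Are matched data likely to exist?**

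Section 5.5 says that bladder thresholds are higher than sphincter thresholds. A setting that empties the bladder should therefore lie above the low-frequency sphincter threshold, and the step-down runs from that setting to threshold. The 600 Hz ramp starts at 0 mA. The two ranges probably overlap, though 5.6 uses neither for a matched contrast.

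**4. The within-run fall at 600 Hz.**

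Onset against plateau in one run is at fixed amplitude. It must use the same summary in both periods. In a simulation with 8 participants, independent noise and no true fall, the peak of 3 onset readings against the mean of 20 plateau readings falsely shows a fall in 76% of studies. Mean against mean over equal numbers of readings gives 2.5%.

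**The case against.** **The design can already answer the question.** Much of this stands. The step-down and ramp probably overlap in amplitude. Holding 600 Hz for up to 30 seconds would show whether pressure falls, and if 600 Hz did nothing it should stay near its onset level. But 5.6 names neither source, and the within-run fall is not the low-frequency comparison.

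**The usual setting is the intended comparator.** This is a fair reading, since 3.0 and 5.6 refer to the frequency that participants typically use. Comparison with usual practice is legitimate. It does not isolate frequency, and it still needs a stated 600 Hz run and window.

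**Participants as own controls implies a participant term.** Agreed. This is an omission from the stated model, not a contradiction of the design.

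**It is an 8-person case series.** True, but 5.6 commits to a significance test, and that test should match the hypothesis.

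A reader might infer more than the documents support:

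- That frequency is confounded with amplitude in this study. Confounding is possible if unmatched runs are compared, but the plan does not say that they will be.
- That the study carries a false-positive rate of 45% to 95%. Those figures belong to an assumed 30-point mismatch in a contrast that the plan does not name, and the direction could be either way.
- That the limitations sentence in 5.6 is a formal failure rule. It has no decision rule attached.
- That there is still time to settle this ahead of testing. The documents do not say whether testing has begun.

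**Conclusion.** The point holds as a mismatch between hypothesis and test, and should be fixed. The omissions in 5.6 are plain from the text: no direct contrast, no choice among the 600 Hz runs, no participant term and no window. That the three-condition test cannot by itself support the hypothesis follows from its form; the 91.5% to 100% rejection under both truths illustrates this for a 50-point contraction and SDs of 20 to 40, all assumed. Amplitude bias is a possibility that the plan leaves open. Its size and direction cannot be given, because recruitment at the usual setting is not in the documents.

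**What to change.** In 5.6, for both aims:

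1. Make the key test a within-participant contrast of 600 Hz against low frequency at an amplitude applied at both frequencies, taken from the existing low-frequency step-down and the 600 Hz ramp or holds. State the matching rule and the 600 Hz runs in advance of analysis.
2. Average pressure over a stated window after the onset response. Take it within stimulation-on periods, since the usual settings to be documented extend to on/off cycling: "including stimulation amplitude, pulse width, frequency, and on/off cycle duration".
3. Keep the pressure and amplitude recordings from the step-down, including the anal channel for Aim 2. Amplitude steps and hold times stay with the investigators.
4. Report 600 Hz against the usual bladder or bowel setting separately, as a comparison with usual practice.
5. Pre-specify the onset-to-plateau fall at 600 Hz as supporting evidence, with the same summary statistic and window length in both periods.
6. Keep the three-condition ANOVA only as an overall test, with a participant term.

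**Cost.** Mainly wording, plus retaining recordings from steps already planned. Some participants will have fewer matched levels. Equal amplitude may not give exactly equal recruitment at the two frequencies: by the second table, a 5-point mismatch would favour 600 Hz in about 5% to 9% of studies with no frequency effect, and a 10-point mismatch in 9% to 23%, if it runs that way. If testing has already begun, the change should be made before analysis.
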